### **Recruitment Procedures**

#### **Describe settings where recruitment will occur**

Cocaine-dependent patients: Most of the recruitment through the STARS clinic occurs through the media. For patients at the Division on Substance Abuse (DOSA) at Albert Einstein College of Medicine, they may participate if they are patients already attending treatment at the Next Step program, or respond to advertisement and present themselves to participate in the study at Waters Place location (affiliated with Albert Einstein College of Medicine). The Next Steps Program is the outpatient substance abuse treatment program affiliated with the Division on Substance Abuse at the Albert Einstein College of Medicine.

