**Select one of the following**

Multicenter (NYSPI is a participating site)

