#### **How and by whom will subjects be approached and/or recruited?**

---

As they are no clinical service at the STARS clinic, all patients that may be eligible to participate in this study will present to STARS in response to media advertising.

For potential patients contacting the STARS clinic or the Division on Substance Abuse at the Albert Einstein College of Medicine (DOSA), a standardized telephone interview is conducted at the first call. Prospective participants who do not present with immediate exclusion criteria are scheduled for a first screening visit. **We have a request for a Waiver of Documentation of Consent for the phone screen under reference 45 CFR 46.117 (c), (1) (2).**

For patients already enrolled in the Next Step program at DOSA, screening may be arranged for patients deemed eligible by their counsellors, or after the patient has voluntarily initiated contact with the investigators. The screening process consists of a psychiatric diagnostic evaluation and a medical evaluation of the candidate to rule out any condition that may make participation in this study hazardous.

The consent procedure for the baseline evaluation differs between the two sites. For patients enrolled through the STARS clinic, they must first read and agree to the general screening consent (NYPI IRB# 4436R) describing the evaluation process in detail. For patients enrolling through DOSA, the screening process is included in the consent form for the study (Einstein IRB# 2014-3568).

The screening process begins with completion of the following forms: locator form; demographic form, drug history questionnaire, concomitant medication form. The locator form indicates the patient's name, address, phone number, as well as names, addresses and phone numbers of family members and close friends, along with a permission to contact them. The demographic form records information about education, marital status, employment, income, social support, housing, gender and racial category. The drug history questionnaire reviews lifetime use of drugs by category, as well as any previous treatment attended.

The psychiatric diagnostic evaluation follows, conducted by a member of the research staff (LCSW, CASAC, MD, PhD) trained in the administration of the Mini International Neuropsychiatric Interview (MINI; Lecrubier et al., 1997), a treatment/drug use history, and a Hamilton Depression Scale – 25 (Williams, 1988).

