Control patients will participate only in phase 1. They will not be hospitalized, but the structure of the testing will be such as to reproduce the conditions under which the cocaine-dependent patients will be tested. When the two consecutive days of testing are completed, their participation ends. These will be matched for age and gender.

Phase 2 follows to study the effects of intranasal oxytocin on relapse risk to cocaine use after abstinence is induced. This phase of the study will be carried out identically at the STARS clinic, or at the Division on Substance Abuse at Albert Einstein College of Medicine. During this phase, patients must attend the clinic three times a week. At these visits, the randomized medication will be taken under supervision of research staff, from a bottle kept at the research site. On the days when the patient is not at the research site, the medication is taken as instructed from an at-home bottle. Compliance with at-home administration will be monitored by a single-blind weighing of the at-home bottle at each visit. At each visit, vital signs, adverse events, urine toxicology, and drug use are reviewed. At one visit, the patient will meet with a counselor for compliance enhancement therapy. At another visit, the patient will meet with a research MD for ratings, monitor progress, and review side-effects.

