### **Clinical Treatment Alternatives**

#### **Clinical treatment alternatives**

This proposal offers procedures that themselves are part of recognized treatment approaches to cocaine dependence. The procedures described here are based in part on protocol 6013, which studies the effects of mifepristone in humans to treat cocaine dependence.

We have used in hospital treatment for detoxification as a well-established method of first intervention in cocaine dependence. It is readily appreciated by most patients that if they could stop on their own, in their own home, they would have done so. Compliance enhancement therapy (Carroll et al., 1994), coupled with voucher incentives (Higgins et al., 1994) provide behavioral treatments with demonstrated efficacy.

If patients contacting STARS cannot qualify, we will offer referrals to clinical treatment. For patients contacting DoSA, participation in the Next Steps program is an option, with or without participation in the study. Patients completing the study can continue at Next Steps.

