14. PROJECT DIRECTOR/PRINCIPAL INVESTIGATOR CONTACT INFORMATION
Prefix: Dr. * First Name: [name] Middle Name: N
* Last Name: [name] Suffix:
Position/Title: Research Scientist level VI
* Organization Name: Research Foundation for Mental Hygiene, Inc.
Department: 110 NYPI Substance Abuse Division:
* Street1: NYPI
Street2: [name]
* City: New York County / Parish: New York
* State: NY: New York Province:
* Country: USA: UNITED STATES * ZIP / Postal Code: 10032
* [contact] [contact]
* Email: [contact]

2) Cocaine Craving Scale (CCS, Weiss et al., 1997); 3) Subjective ratings of cocaine craving, depression, anxiety, stress during stress testing (Likert scale 0 to 10, 10 = worse) Physiological tests: 1) Nine drug urine toxicology (Iscreen™ 9 drugs); 2) Stress Sensitivity Testing: serum ACTH, HR, BP for Day 1 and Day 2 (see table 2.)

Phase 2 Measures: The goal of phase 2 is to test if IN OT can reduce relapse risk. Measures collected may inform *Primary Aim 2, Secondary Hypotheses, and Exploratory Aims a, b* (section 3.4). **Compliance monitoring:** a) Witnessed, and recorded insufflations of IN OT vs. Pbo, 3x/wk from a bottle kept refrigerated at STARS; b) Patients will be instructed on storing and using the nasal spray bottle before At-home insufflation begins. They will be told to bring this bottle with them at every visit. [*Monitoring: unbeknownst* to the patient, the at-home bottle will be weighed before being given, and will be weighed at every visit. The metered bottle delivers 5 IU/0.1cc or per puff. Each daily dose requires 4 puffs or 0.4 cc. The weight of each puff or 0.1cc is approximately 0.1g, hence for each at-home insufflation, the bottle weight is expected to change by 400 mg. The expected weight change will be compared to the actual recorded weight.] **Medical monitoring:** a) electrolyte: (Na, K, Cl), spot cortisol, urine pregnancy test for women at week 2, 4, 6; b) weekly medical review for signs and symptoms of hyponatremia and side effects. **Clinician Interviews:** 1) TLFB 3x/wk; 2) CGI-O 1x/wk; 3) Adverse event form 3x/wk; 4) HamD 1x/wk. **Self reports:** 1) PSS 1x/week, 2) CCS 3x/week. 3) subjective ratings of depression, anxiety, stress and cocaine craving (Likert scale 0 to 10) and BAS (table 2). **Physiological tests:** *Stress sensitivity testing:* repeat of Day 1 IN DDAVP 80 IU challenge, ACTH, HR, BP; 2) *Nine drug urine toxicology, 3x/wk.*

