
3.3 Compensation and data management.

For phase 1, control participants will receive \$150 for their participation; cocaine-dependent patients will receive \$20/day, or will receive \$150 if they complete the whole week. [During phase 2, cocaine-dependent patients accumulate vouchers for completing all study procedures (Bringing home bottle, assessments, study visits).] Each visit with all study procedures completed will earn them \$5. They can also earn \$20 for each week of consecutive and complete participation. Transportation costs are covered (\$5/visit). Total earnings can reach \$450. StudyTrack, a software system for clinical trials will be used for data management.

3.4 Statistical Analysis:

3.4.1. Outcome measures: PHASE 1: **Primary outcomes:** 1) secretion of ACTH (continuous measure of area from the concentration-time curve (AUC) using trapezoid method, pg/mL/min). 2) subjective rating of cocaine craving, stress, depression, anxiety (continuous) 3) difference in ACTH secretion between IN DDAVP (day 1) and IN OT prior to IN DDAVP (day 2) (continuous measure); 4) difference in subjective rating of cocaine

craving, stress, depression, anxiety between IN VP (day 1) and IN OT prior to IN DDAVP (day 2; continuous, controlled for last day of use before entering Phase 1); **PHASE 2: Primary outcome:** 1) maximum number of consecutive abstinent days (continuous measure) ; **Secondary outcome:** 1) cocaine using days (continuous). **Covariates/Predictor Variables:** demographics, age, gender; cocaine data (TLFB, 30 days; IN vs. smoked).

3.4.2. Sample size: In PHASE 1, we will enroll a total of 100 participants: 1) Cocaine group (COC): Cocaine-dependent patients seeking treatment (n=50); 2) Control group (CON): Healthy matched controls (n=50), each matched demographically (see 3.1.1). In PHASE 2, we will randomize the 50 COC patients into two groups: 1) Oxytocin group (OT), n=25; 2) Placebo group (PBO), n=25. An independent statistician will perform, and an independent pharmacist will implement the randomization. Individuals will be stratified by route of cocaine use. The randomization will be balanced in blocks of random size 2 and 4 to prevent compromise of the blind.

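### Phase 2 runs at two sites, one of which may enrol patients already in an addiction treatment program, but neither site nor that enrolment is a stratum, a candidate covariate or a model term

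*Protocol*

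**What the plan says.** **Sites.** The protocol's funding section classes the trial as multicentre. On Phase 2, the Design Overview says: "This phase of the study will be carried out identically at the STARS clinic, or at the Division on Substance Abuse". The second of these is the Einstein site. The Phase 2 procedures set out one program of visits, witnessed dosing, therapy and vouchers for both clinics.

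**Who is enrolled.** Under Recruitment Procedures, STARS patients all come through media advertising: "As they are no clinical service at the STARS clinic". DOSA patients may answer advertising too, but "they may participate if they are patients already attending treatment at the Next Step program", which the protocol describes as an outpatient substance abuse treatment program. Counsellors there may identify patients for screening. Under Clinical Treatment Alternatives, for patients contacting DOSA, "participation in the Next Steps program is an option, with or without participation in the study". The section on treatment at the end of the study says that patients in the program can stay in it. No listed exclusion criterion bars concurrent addiction treatment.

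**Analysis.** The SAP text provided names one clinic: under Phase 2 Measures, supervised doses come "from a bottle kept refrigerated at STARS". On randomisation, SAP 3.4.2 says: "Individuals will be stratified by route of cocaine use". SAP 3.4.1 lists the candidate covariates as demographics, age, gender, and baseline cocaine data including route. SAP 3.4.4 admits covariates from that list if they turn out to affect outcome. The Primary Aim 2 model names the arm effect only. The reported Wilcoxon test compares arms only.

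**The concern.** Next Step treatment is aimed at cocaine use, which is what the primary Phase 2 outcome measures. The documents describe it at one site only, and only some patients at that site will be in it. Phase 2 patients may therefore differ in background care by site and, within DOSA, by enrolment. If that care lengthens abstinent runs, leaving it out has two consequences. Its contribution stays in the residual variance and lowers power. And if the arms happen to differ in the share of such patients, a reader cannot separate that difference from the effect of the spray. Because SAP 3.4.1 closes the covariate list, the SAP offers no route to examine either factor.

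**Working it through.** **Inputs from the documents.** Planned allocation 25 vs 25; two-sided 5%; effect size 0.8; at least 80% power (SAP Power Analysis). Reported allocation 15 vs 11 (SAP, Primary outcome).

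**Inputs that are assumptions.** The share of patients in Next Step (20-50%) and its effect on the outcome (0.3, 0.5 or 0.8 SD). The documents give neither.

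**1. The plan's power figure.** The noncentrality is 0.8 / √(1/25 + 1/25) = 2.828. By the normal approximation, power = Φ(2.828 − 1.960) = 80.7%. By the noncentral t with 48 df (critical t 2.011), it is 79.1%. The stated figure reproduces within about a point and is not in dispute. Neither calculation has a site or co-treatment term.

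**2. Chance imbalance of a binary baseline factor outside the strata.** With K of N patients carrying the factor and n₁ of N in the first arm, the number X carrying it in that arm is hypergeometric: P(X = x) = C(K, x)·C(N − K, n₁ − x) / C(N, n₁). Sum over all x with |x/n₁ − (K − x)/n₂| ≥ 0.20. The route strata are ignored.

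| Assumed share | 25 vs 25: K, probability | 15 vs 11: K, probability |
|---|---|---|
| 20% | 10, 7% | 5, 13% |
| 30% | 15, 22% | 8, 39% |
| 40% | 20, 15% | 10, 23% |
| 50% | 25, 26% | 13, 43% |

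The values do not rise steadily because counts are whole numbers. At 15 of 50, for example, splits of 6 to 9 in one arm differ by at most 12 points, and the next split (5 vs 10) differs by exactly 20.

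**3. What a 20-point imbalance does.** The unadjusted arm difference moves by 0.20 × the factor's effect: 0.06, 0.10 or 0.16 SD for effects of 0.3, 0.5 or 0.8 SD.

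**4. Power with adjustment.** Let the factor have share p and effect D, in units of the SD within its levels. Adjustment multiplies the effect size by √(1 + p(1 − p)D²) and leaves 47 df.

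- D = 0.5, p = 0.3: √1.0525 = 1.026; power 81.1%.
- D = 0.5, p = 0.5: √1.0625 = 1.031; power 81.5%.
- D = 0.8, p = 0.3 to 0.5: power 83.9-84.7%.

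Each compares with 79.1% unadjusted. If the 0.8 is instead read in within-level SD units, adjusted power is 79% and unadjusted power is 73-79% over shares of 20-50% and effects of 0.3-0.8 SD. At 15 vs 11, the gain for D = 0.5 and p = 0.3 to 0.5 is from 49% to about 51%.

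These figures use a normal outcome as an approximation. They also describe adjustment for the factor itself. Site captures Next Step enrolment only in part, because DOSA takes advertisement responders as well.

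**The case against.** The strongest reply is that nothing here threatens validity. Arms are randomised and blinded, so background care is independent of arm in expectation, and the 5% error rate of the unadjusted test already allows for chance imbalance in baseline factors. The design also narrows the differences between patients: all must have a cocaine-positive urine at screening, reach abstinence before Phase 2, and receive the same study therapy and vouchers. The content and intensity of Next Step are not described, so its added effect is unknown. The power gain is about 2 points under an assumed effect. The larger gain needs a Next Step effect of 0.8 SD, as big as the effect the trial was sized to detect. All of this stands, and it limits the point to precision and interpretation.

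Four stronger readings are tempting, and the documents do not support them.

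- **That the omission biases the oxytocin estimate.** Randomisation rules out a systematic shift.
- **That a serious imbalance is likely.** Every probability above is below one half, and at the planned size the highest is about one in four.
- **That the SAP was written for a single-site trial.** That would rest on one phrase about where a bottle is kept. The text is an extract of a grant application, and section 3.1.1, to which it refers, is not shown.
- **That the protocol is wrong to call Phase 2 identical at the two sites.** That word describes study procedures, which are set out once for both clinics. Care outside the study does not contradict it.

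The objection does not meet one fact: the covariate list is closed, and both factors lie outside it.

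**Conclusion.** The point holds as a gap in the analysis plan that is cheap to close. The two Phase 2 sites have different enrolment sources, only DOSA is described as enrolling patients already in addiction treatment that may continue, and the SAP's stratum, covariate list, model and reported test leave out both site and that treatment.

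The size is modest and rests on assumptions. For shares of 20-50%, a 20-point imbalance has probability 7-26% as planned and 13-43% as reported. With a 0.5 SD effect, such an imbalance moves the estimate by 0.10 SD, and adjustment gains about 2 points of power at shares of 30-50%. The reported null result is not shown to be wrong. What is missing is any means of seeing whether background treatment was balanced between 15 and 11 patients.

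**What to change.** - **Primary Phase 2 model.** Add site (STARS or DOSA) as a fixed term beside treatment. If a rank test is kept, use the van Elteren test stratified by site.
- **Sensitivity analysis.** Adjust also for Next Step enrolment at entry. Do not adjust for attendance that begins after randomisation: the program is open to anyone contacting DOSA, so later attendance could itself depend on the assigned treatment.
- **Reporting.** Tabulate site and Next Step enrolment at entry by arm.
- **The 26 patients already analysed.** Label any such adjustment a post hoc sensitivity analysis, since it can no longer be prespecified.

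The site term costs one degree of freedom: at 25 per arm the critical t goes from 2.011 (48 df) to 2.012 (47 df). Site is known for every patient. Next Step status at entry has to be recorded explicitly, a small addition to a screening process that already takes treatment history. Site should not become a further randomisation stratum, because at this sample size that would leave many incomplete blocks. The protocol's description of Phase 2 as identical at the two sites needs no change.

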#### **How and by whom will subjects be approached and/or recruited?**

---

As they are no clinical service at the STARS clinic, all patients that may be eligible to participate in this study will present to STARS in response to media advertising.

For potential patients contacting the STARS clinic or the Division on Substance Abuse at the Albert Einstein College of Medicine (DOSA), a standardized telephone interview is conducted at the first call. Prospective participants who do not present with immediate exclusion criteria are scheduled for a first screening visit. **We have a request for a Waiver of Documentation of Consent for the phone screen under reference 45 CFR 46.117 (c), (1) (2).**

For patients already enrolled in the Next Step program at DOSA, screening may be arranged for patients deemed eligible by their counsellors, or after the patient has voluntarily initiated contact with the investigators. The screening process consists of a psychiatric diagnostic evaluation and a medical evaluation of the candidate to rule out any condition that may make participation in this study hazardous.

The consent procedure for the baseline evaluation differs between the two sites. For patients enrolled through the STARS clinic, they must first read and agree to the general screening consent (NYPI IRB# 4436R) describing the evaluation process in detail. For patients enrolling through DOSA, the screening process is included in the consent form for the study (Einstein IRB# 2014-3568).

The screening process begins with completion of the following forms: locator form; demographic form, drug history questionnaire, concomitant medication form. The locator form indicates the patient's name, address, phone number, as well as names, addresses and phone numbers of family members and close friends, along with a permission to contact them. The demographic form records information about education, marital status, employment, income, social support, housing, gender and racial category. The drug history questionnaire reviews lifetime use of drugs by category, as well as any previous treatment attended.

The psychiatric diagnostic evaluation follows, conducted by a member of the research staff (LCSW, CASAC, MD, PhD) trained in the administration of the Mini International Neuropsychiatric Interview (MINI; Lecrubier et al., 1997), a treatment/drug use history, and a Hamilton Depression Scale – 25 (Williams, 1988).

The psychiatric evaluation is conducted by a research psychiatrist (MD). It includes a psychiatric and medical review of systems, a mental status examination, a review of inclusion/exclusion criteria, and of the diagnostic evaluation. A consensus diagnosis is reached, which must include cocaine dependence, and not include any exclusion diagnoses.

The MD then conducts the medical evaluation, including: medical history, review of systems, physical examination including vital signs, olfactoscopic examination of the nasal cavity, screening blood test (chem-20, CBC, urinalysis, urine toxicology, urine pregnancy test for women patients), and an electrocardiogram. The Scent test is conducted at this point.

When completed, and the laboratory reports received, the assembled information is reviewed by the principal investigator or a research MD familiar with the study protocol. This information is reviewed against the inclusion/exclusion criteria of the study to determine eligibility to participate. For control participants, the screening process is the same as described for cocaine-dependent patients. For potential control participants entering through the STARS clinic, they will sign the

screening consent form (IRB# 4436R). Those entering through DOSA, they will sign the study consent form for control participants (Einstein IRB# pending)

**How will the study be advertised/publicized?**

This study will be advertised through print media such as the village voice, Metro AM, AM NY. Once prospective patients or control participants call, they will be offered to screen either at DOSA, or at STARS. AT DOSA, Albert Einstein College of Medicine IRB-approved flyers will be posted in the clinic.

**Do you have ads/recruitment material requiring review at this time?**

Yes

**Does this study involve a clinical trial?**

Yes

**YOU MUST REGISTER AT [ClinicalTrials.gov](http://ClinicalTrials.gov) IMMEDIATELY UPON RECEIPT OF IRB APPROVAL AND PRIOR TO ENROLLMENT OF THE FIRST SUBJECT. YOU WILL BE PROVIDED WITH A NCT REGISTRATION NUMBER ON REGISTRATION. PLEASE REVISE THIS SECTION OF THE PROTOCOL SUMMARY FORM TO INCLUDE THE NCT NUMBER AND RE-SUBMIT AS AN AMENDMENT TO THE IRB.**

**Concurrent Research Studies**

**Will subjects in this study participate in or be recruited from other studies?**

No

**Inclusion/Exclusion Criteria**

**Name the subject group/sub sample**

cocaine-dependent sample

**Create or insert table to describe the inclusion criteria and methods to ascertain them**

INCLUSION CRITERION	METHOD OF ASCERTAINMENT
1.Age 18 to 60.	MINI interview, self-report, ID confirmation
2. Meets DSM IV criteria for current cocaine	MINI Interview, self

dependence and is seeking treatment.	report
3. Displays at least one cocaine-positive urine toxicology during screening.	Urine Toxicology
4. Use of cocaine at least 4 days in the past month, with at least weekly use, or reports episodic binges of large amounts of cocaine (at least \$200) at least 2x/month.	Self report
5. Able to give informed consent and comply with study procedures.	MINI, Self-report, MSE
6. Can pass the blindfolded scent test recognizing the scent of cinnamon or coffee.	Scent test

